### **Background and Rationale**

Pacific Islanders residing in the United States (US) have disproportionally higher rates of preterm birth (<37 completed weeks) and low birthweight infants (<2,500 grams). They are also more likely to experience preeclampsia, primary cesarean birth, excessive gestational weight gain, gestational diabetes mellitus (GDM) and low exclusive breastfeeding initiation and duration at six months compared to other racial/ethnic minorities and the US population in general.  Preterm birth is a pressing challenge to maternal, infant, and child health in the US because preterm infants can face lifelong disabilities and are at higher risk of death during their first few days of life.  Early and consistent prenatal care is strongly associated with positive birth outcomes and is a global health priority.  However, Pacific Islanders, are less likely to receive early and consistent prenatal care compared to other racial/ethnic groups and are thus at a higher risk for maternal and infant health disparities. 

Pilot analysis of Arkansas birth records (n=2,488) has shown that Marshallese in Arkansas experience a high rate of adverse perinatal outcomes: 15% of Marshallese women received no prenatal care (compared to 1.6% women nationally); More than 50% do not attend the recommended number of prenatal care visits; 19% of Marshallese infants were born preterm (compared to 9.6% nationally), and 15% of Marshallese infants were low birthweight (compared to 8.3% nationally). Additionally, qualitative data, demonstrate that Marshallese women experience numerous structural barriers that constrain prenatal care such as negotiating health insurance, transportation, and language barriers. Social-cultural barriers include a lack of understanding of the importance of seeking early and consistent prenatal care, feelings of shame and embarrassment, perceived discrimination from prenatal care providers, and an overall fear of the process.

Current health care interventions are not culturally relevant or focus primarily on individual-level motivations that are not effective within highly collectivistic Pacific Islander cultures.  Pacific Islander communities' concepts of health and wellbeing are largely shaped by collectivistic cultural values and practices, suggesting the need for culturally adapted group-based interventions.  Recent data with other cultural groups report that pregnant women who received a group-based prenatal intervention (Centering Pregnancy) had a significantly lower risk of having a preterm birth, low birth weight infants, and improved outcomes with GDM compared to women receiving individualized care.  However, group prenatal care has not been culturally adapted and tested with the Marshallese or other Pacific Islanders in the mainland US.

From 2000 to 2010, the Pacific Islander population in the US increased by 40%, growing three times faster than the total US population and making it the second-

 Version #:10
 Page 3

 Date: 20250403
 IRB#261186

Maternal and Infant Health Outcomes of Marshallese in Arkansas

PI: [name]

Institution: University of Arkansas for Medical Sciences Northwest Campus

fastest-growing population in the US. The fastest growth occurred in the South (66%), especially in Arkansas (252%), where the majority of Pacific Islanders are Marshallese. Arkansas has the largest population of Marshallese living in the continental US (~14,000 people). Since the Pacific Islander population is small, some argue that the Pacific Islander population should be given less consideration for funding than other racial and ethnic groups; this faulty logic has directly contributed to the stark health disparities experienced by this population. Pacific Islanders are underrepresented in research and receive far less investment than other disparate populations (both in total and in proportion to their population numbers). Overall, limited scientific knowledge, masked health disparities due to data aggregation of Pacific Islanders with other Asian groups, and a lack of resource allocation for research and programs are critical barriers to progress in addressing Pacific Islanders' health disparities.

To design a culturally appropriate group prenatal intervention among Marshallese and other Pacific Islanders in the US, it is necessary to understand Marshallese culture and the historical relationship between the Republic of the Marshall Islands (RMI) and the US. Between 1946 and 1958, the US tested nuclear weapons in the Marshall Islands. Tests were equivalent to 7,200 Hiroshima-sized bombs and exposed islanders to significant levels of nuclear radiation. 35-38 After the nuclear tests, US scientists set up Project 4.1 to study the effects of nuclear radiation on humans. 39-42 The research was conducted without informed consent and without language translation. Studies demonstrate health problems affecting those exposed and changes in Marshallese health behaviors. 43-46 Like other cultures marked by historical trauma, the Marshallese exhibit distrust in researchers. The research team is overcoming this historical trauma through the use of a community-engaged research (CER) approach. CER shares power and builds trust between academic researchers and the community. The research is based on an academic-community partnership between the University of Arkansas for Medical Sciences (UAMS) and the Marshallese community. 52-54 The historical trauma makes the use of a CER approach key to the proposed research. Furthermore, there is evidence that utilizing behavioral interventions validated in one Pacific Islander group can be effective in other Pacific Islander populations. Establishing the evidence-base for interventions designed for Pacific Islanders may also inform work with other disenfranchised and indigenous populations who have strong collectivist cultures, thus increasing the generalizability of the proposed research. 55-59

The purpose of the study is to culturally adapt and examine the feasibility of a group prenatal program (Kōmmour Prenatal) to reduce maternal and infant health disparities among Marshallese women in the US. The word "kōmmour" signifies a healthy birth or a

Version #:10 Page 4
Date: 20250403 IRB#261186

Maternal and Infant Health Outcomes of Marshallese in Arkansas

PI: [name]

Institution: University of Arkansas for Medical Sciences Northwest Campus

healthy start in the Marshallese language and was the name chose by the Marshallese advisory board for this study.

### **Specific Aims**

**Aim 1:** Adapt a group-based prenatal intervention for pregnant Marshallese mothers (Kōmmour Prenatal) through culturally adapting an evidence-based prenatal intervention (Centering).

**Aim 2:** Conduct a feasibility/pilot test of Kōmmour Prenatal with up to 100 pregnant Marshallese women in Arkansas.

Aim 3: Compare the effectiveness on maternal and infant health outcomes between up to 100 pregnant Marshallese women provided Kōmmour Prenatal with the maternal and infant health outcomes of up to 100 pregnant Marshallese women who received individualized prenatal care. The provision of Kōmmour Prenatal is expected to demonstrate improved primary outcome of Gestational Weight Gain (GWG) and secondary outcomes of breastfeeding initiation; birthweight of infant, preeclampsia; primary cesarean birth; and GDM.

**Aim 4:** Explore the barriers and facilitators experienced by Clinical Staff and Marshallese Stakeholders who participate in the implementation of Kōmmour Prenatal with Marshallese women in Arkansas.

### **Study Design and Procedures**

A mixed methods design will be utilized to explore the feasibility and preliminary effectiveness of Kōmmour Prenatal among pregnant Marshallese women. Potential participants may be recruited from UAMS centering programs, including mobile centering, across the state.

Participants will be invited to take part in a focus group and survey prior to attending up to 10 group prenatal sessions (Kōmmour Prenatal). Participants will also be invited to take part in both the survey and qualitative focus groups at the end of the intervention. The surveys will capture demographics, health behavior and health belief information. The focus groups will focus on beliefs and experiences of individualized and group prenatal care, prenatal care satisfaction, and health behaviors. Study procedures (e.g., consent process, focus groups, surveys, data collection, administering compensation) will be conducted in person or remotely. In either case, tools such as phone, video, email, text, and online data collection tools (e.g., REDCap) may be used.

Due to difficulty with in-person data collection, remote date collection via Zoom will be utilized to collect focus groups and surveys when in-person data collection is not feasible for the participant.

 Version #:10
 Page 5

 Date: 20250403
 IRB#261186

Maternal and Infant Health Outcomes of Marshallese in Arkansas

PI: [name]

Institution: University of Arkansas for Medical Sciences Northwest Campus

To reduce the participant burden, information regarding birth and/or death outcomes and other variables may be collected up to 7 years post-delivery and linked to the participant and her child(ren) from one of the following sources: (1) the mother's electronic medical record at UAMS; (2) the Arkansas Department of Health (ADH) birth and/or death records; (3) the Arkansas All Payers Claims Database (APCD); or (4) via a release of information signed by the mother for babies delivered outside of UAMS. The consent document will include consent for each of these sources. Data collected from these sources may include: general contact and background information about (such as name, address, and telephone number), living situation, income, educational background, maternal medical history, and birth outcomes (gestational age, birth weight, complications, etc). A complete list of data that may be collected from the ADH is attached to this protocol in Appendix 1. Participants will be asked to acknowledge their understanding of this data collection at the time of consent. Participants will have the opportunity to choose if they wish to be re-contacted for future research at the time of consent.

In addition, data from this study will be linked to vital birth record information from the Arkansas Department of Health. Participants will be asked to acknowledge their understanding of this data collection at the time of consent. Data collected from the Arkansas Department of Health may include, but is not limited to: demographic and socioeconomic information, maternal medical history, and birth outcomes (gestational age, birth weight, complications, etc). Because data from birth records is aggregated, data from the Arkansas Department of Health will provide disaggregated data so that covariates (demographic and socioeconomic variables) can be used in the analyses.

Participants will have the opportunity to choose if they wish to be re-contacted for future research at the time of consent.

We will collect the following information via medical record abstraction:

For Marshallese participants who are pregnant:

- date of first prenatal care visit
- number of prenatal care visits
- fasting glucose
- weight and height
- blood pressure
- gestational weeks at delivery
- complications

 Version #:10
 Page 6

 Date: 20250403
 IRB#261186

Maternal and Infant Health Outcomes of Marshallese in Arkansas

PI: [name]

Institution: University of Arkansas for Medical Sciences Northwest Campus

- gestational diabetes mellitus
- infant feeding intentions

For infants of Marshallese participants

- date of birth
- size of infant
- weight and height
- complications

Participants will be given the opportunity to separately consent to allowing investigators to link their data to the Arkansas All-Payer Claims Database (APCD). For those participants that provide consent, investigators will analyze the cost of participants care relative to their risk factors. The research team may analyze outcomes across multiple studies if participants provide permission in the consent process.

Qualitative data will be collected from up to 100 participants in focus groups. A semistructured focus group guide will be used to allow participants to speak in-depth about their health beliefs and experiences, yet also ensure that all focus groups cover the same topics. The focus group guides were developed in partnership with communitybased participatory research (CBPR) stakeholders and from information gained through fieldwork. Focus groups will have an anticipated duration of one hour.

In addition, we will collect data from up to 10 clinical staff and/or Marshallese stakeholders who participated in the implementation of the group prenatal program for Marshallese women. Clinical staff and/or Marshallese stakeholders will participate in one individual interview and one demographic survey. Data collection will take place at the end of the interventions duration.

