## Study Schedule for women in Kommour Prenatal

For pregnant women enrolled in Kōmmour Prenatal, the first survey and focus group will take place at enrollment. Participants will attend up to 10 group prenatal sessions. Another survey and focus group will take place in the third trimester (6-9 months of pregnancy). Data abstraction from birth and medical records will take place after the birth for information of both the postpartum participant and her infant.

Data Collection-Pregnant Women in Kommour Prenatal

 Version #:10
 Page 7

 Date: 20250403
 IRB#261186

Maternal and Infant Health Outcomes of Marshallese in Arkansas

PI: [name]

Institution: University of Arkansas for Medical Sciences Northwest Campus

Enroll	First trimester	Second Trimester	Third trimester	Six Weeks Postpartum
Enrolled in study	X	Х	Х	
10 Group-Prenatal Intervention	Х	Х	Х	
Medical record abstraction	Х			Х
Birth record abstraction				Х
Focus group	Х	Х	Х	
Survey questionnaire	Х	Х	Х	

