## **Study Timeline**

Study initiation is planned for January 2021 with a duration of five years (60 months). Focus group guides and survey adaptation will take place in months 1-3. Enrollment will take place in months 4-16. Participants will attend up to 10 group prenatal sessions. The last participant enrolled will have time for final data collection prior to the end of the study at 60 months.

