### **Data Handling and Recordkeeping**

The principal investigator will carefully monitor study procedures to protect the safety of research subjects, the quality of the data and the integrity of the study. All study subject material will be assigned a unique identifying code or number. The key to the code will be kept in a locked file cabinet in a locked file room in the Office of Community Health and Research. Only the principal investigator and the study coordinator will have access to the code and information that identifies the subject in this study. At the conclusion of the study, the data will be permanently de-identified.

The study will comply with UAMS Admin Guide Policy 3.2.01 – research data, reports and analyses be retained for seven years after final reporting or publication of a project, or longer if required by a sponsor or regulation.

 Version #:10
 Page 9

 Date: 20250403
 IRB#261186

Maternal and Infant Health Outcomes of Marshallese in Arkansas

PI: [name]

Institution: University of Arkansas for Medical Sciences Northwest Campus

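### Does permanent de-identification at the end of a 60-month study defeat the permission to link records for up to 7 years after delivery?

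*Combined protocol and SAP*

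**What the plan says.** Four parts of the protocol bear on this.

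- **Study Design and Procedures** lists four sources (UAMS records, state birth and death records, the claims database, and releases for deliveries outside UAMS). It says that information from them "may be collected up to 7 years post-delivery and linked to the participant and her child(ren". The same section plans an analysis of the cost of care among women who consent to claims linkage, with no stated time horizon.
- **Study Timeline** sets 60 months from January 2021. "Enrollment will take place in months 4-16", and "The last participant enrolled will have time for final data collection prior to the end of the study at 60 months".
- **Study Schedule for women in Kommour Prenatal** says: "Data abstraction from birth and medical records will take place after the birth for information of both the postpartum participant and her infant". The last column of its table is six weeks postpartum.
- **Data Handling and Recordkeeping** says: "The key to the code will be kept in a locked file cabinet in a locked file room", and later: "At the conclusion of the study, the data will be permanently de-identified". It cites an institutional policy that "research data, reports and analyses be retained for seven years after final reporting or publication of a project". It does not define conclusion and gives no retention period for the key.

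**The concern.** Linking a new death record or claim to a particular mother and child needs the code key. Once the data are permanently de-identified, that link is gone. A window of seven years after delivery does not fit inside a five-year study that ends with identifiers removed, so the plan seems to permit something that it then makes impossible.

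If that were a real conflict, staff would face a choice. They could let the later part of the linkage lapse, or they could link after the study had concluded and so depart from the section on which Risks and Benefits rests its confidentiality assurance. The step cannot be undone. The seven-year retention policy does not rescue the position: it covers data, reports and analyses rather than the key, and its clock runs from final reporting or publication, not from delivery.

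**Working it through.** **Inputs.** Study length: five years (Study Timeline). Linkage ceiling: 7 years after delivery (Study Design and Procedures). Enrolment: months 4 to 16 (Study Timeline). Women must be pregnant at enrolment (Inclusion Criteria), so delivery cannot come before it. Last scheduled abstraction: six weeks postpartum (Study Schedule).

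**The plan's own figure.** 5 × 12 = 60 months, as stated.

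**Ceiling in months.** 7 × 12 = 84.

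**Linkable time if conclusion means month 60.** With delivery d months after study start, linkable time is 60 − d and the shortfall is 84 − (60 − d) = 24 + d.

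| Delivery | d | Linkable (months) | Short of 84 by |
|---|---|---|---|
| First day of the study (bound) | 0 | 60 | 24 |
| Start of month 4, delivery at enrolment | 3 | 57 | 27 |
| End of month 16, delivery at enrolment | 16 | 44 | 40 |
| End of month 16, 9 months to delivery (assumed) | 25 | 35 | 49 |

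The first row needs no assumption about enrolment or gestation: 60 is less than 84. The ceiling is therefore out of reach for every Kōmmour Prenatal participant on this reading. Comparison women come from earlier studies and their delivery dates are not given, so they are outside this calculation.

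**Does anything scheduled fall after month 60?** Take the latest delivery in the table, d = 25. Six weeks is 6 / 4.348 = 1.4 months, so the last scheduled abstraction is at about 25 + 1.4 = 26.4 months. That is 60 − 26.4 = 33.6 months before the planned end.

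**Does any stated analysis need records from beyond month 60?**

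- The primary outcome (gestational weight gain) and the five secondary outcomes (breastfeeding initiation, birthweight, preeclampsia, primary cesarean, gestational diabetes) are pregnancy, birth or early postpartum measures. All fall inside the schedule above.
- Deaths appear in no aim and in no outcome under Data collection for Aim 3. The variables listed in Appendix 1 stand under a birth heading (the appendix carries a placeholder comment).
- The cost analysis has no stated horizon. With identifiers held to month 60 there are 35 to 57 months of claims per woman on the table's assumptions. Nothing in the protocol says that this is too little.

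**Are the sections incompatible?** Collecting to month 60 and then de-identifying satisfies the ceiling, the timeline and the de-identification rule together. The only thing lost is the unused part of an optional window.

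**The case for a change.** The strongest case for acting is that a ceiling nobody can reach is misleading, above all in a community whose history the Background gives as a reason for distrust of researchers. Women are asked at consent to acknowledge this data collection, so how long families stay identifiable should be plain. The timeline names month 60 as the end of the study, and the current version offers no other meaning for conclusion. A sentence or two would settle the matter, whereas de-identification done too early is irreversible.

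Part of this stands. The term is undefined, the key has no stated retention period, and month 60 is the more natural reading. The retention policy does not fill that gap.

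The rest does not carry a change. The wording grants permission up to a limit, and using less of it breaks no undertaking visible in the protocol. Reading conclusion as the point at which permitted collection has ended would also reconcile the sections, although the protocol does not say that either. The consent pages were not available for review, so silence in the protocol does not show that participants were told nothing about how long identifiers are kept. If the team wants later records, Ethical Considerations already provides for amendments. Keeping the key until the ceiling expires would also have a cost: identifiers would be stored beyond month 60 for records that no stated aim is shown to need.

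**Conclusion.** The mismatch is real but minor. If conclusion means the planned month 60, linkage stops at most 60 months after delivery (57 with enrolment from month 4) against a permitted 84. That shortfall of at least 24 months, or 27 with enrolment from month 4, is in a permitted maximum and not in scheduled follow-up. Following the plan as written leaves the primary outcome, all five secondary outcomes and every stated analysis as sound as before. Limiting the window to the study's end, or defining conclusion, would only reword the text. Holding the key longer would trade confidentiality for data without a stated use. No change to the plan is needed, and the team can settle what counts as conclusion when it closes the study.

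This rests on the planned dates, since actual start and enrolment dates are not in the protocol, and on the stated aims. It would need another look if an analysis that depends on later death or claims records were added.

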## Study Schedule for women in Kommour Prenatal

For pregnant women enrolled in Kōmmour Prenatal, the first survey and focus group will take place at enrollment. Participants will attend up to 10 group prenatal sessions. Another survey and focus group will take place in the third trimester (6-9 months of pregnancy). Data abstraction from birth and medical records will take place after the birth for information of both the postpartum participant and her infant.

Data Collection-Pregnant Women in Kommour Prenatal

 Version #:10
 Page 7

 Date: 20250403
 IRB#261186

Maternal and Infant Health Outcomes of Marshallese in Arkansas

PI: [name]

Institution: University of Arkansas for Medical Sciences Northwest Campus

Enroll	First trimester	Second Trimester	Third trimester	Six Weeks Postpartum
Enrolled in study	X	Х	Х	
10 Group-Prenatal Intervention	Х	Х	Х	
Medical record abstraction	Х			Х
Birth record abstraction				Х
Focus group	Х	Х	Х	
Survey questionnaire	Х	Х	Х	

## **Study Timeline**

Study initiation is planned for January 2021 with a duration of five years (60 months). Focus group guides and survey adaptation will take place in months 1-3. Enrollment will take place in months 4-16. Participants will attend up to 10 group prenatal sessions. The last participant enrolled will have time for final data collection prior to the end of the study at 60 months.

